### **11.2.4 Internal Safety Committee**

An internal safety review committee will review the safety data collected during the study in a blinded manner. The committee members will include study medical monitor, Raziel's CMO and clinical director.

The meeting will be held when every enrolled 40 subjects completed Day 7. Summary of the safety including all subjects up to that point may be reviewed as well. Following completion of enrollment of all subjects, the committee will meet quarterly during the follow up period.

The study enrollment will be suspended if either of the following occur:

- Greater than 20% of subjects report a drug related grade 3 (severe) adverse event for a period duration of more than 28 days after injection. Of note severe swelling is may be during the first 24 – 96 hours after injection.
- >1 subject with a drug related CTCAE Grade of 4 or 5

In the event of the above, the enrollment and treatment will be suspended, the safety committee will review all data to examine potential safety issue. Additional experts may be brought in to review safety data if deemed necessary by the safety committee. A safety report will be issued with the conclusions of the meeting. The recommendation of the safety committee will be documented. Potential outcomes are reinitiating enrollment with current safety practices, reinitiating study with caveats (e.g. additional precautions/limitations or safety training), stop enrollment.. For each internal safety committee meeting, report will be prepared by the medical monitor that include data about enrollment, list of SAEs, summary of AEs.

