#### 1.2.4. Clinical Studies

RZL-012 has been tested in several clinical trials. A total of 92 subjects were exposed to RZL-012 at single doses of up to 240 mg. The currently planned clinical trial is the second trial to assess the potential efficacy of RZL-012 in reducing SMF volume.

Five studies have been completed and efficacy analysis was completed to 4 out of the 5 studies.

Safety analysis of all studies demonstrated that 91/92 subjects had adverse events (AEs). None of the studies was reported with serious AEs. Most of AEs were mild to moderate and were associated with local injection site reactions. Only 10 subjects were reported with severe AEs (7% of the reported events).

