Baseline treatment period: A total of 135 eligible male or female subjects will be randomized according to a predetermined randomization scheme (1:1:1 ratio) to receive a single multi-injection treatment of high dose RZL-012, low dose RZL-012, or placebo on Day 0. Subjects will be monitored for AEs and treatment area evaluation for 30 minutes post dose prior to discharge from the clinical trial site. Subjects will return to the site for study visits on Days 1, 7, 28, and 56 and for a final study visit on Day 84 for efficacy and safety assessments.

Subjects will be advised to continue their regular diet and physical activity during the study.

Blood samples will be collected at Day 1, 7, 28 and Day 84 study visits for assessment of hematology and serum chemistry. If there are clinically significant alerts obtained at any visit, , an unscheduled visit will be added for additional blood sampling.

Safety assessments will be performed at each study visit and subjects can be released after blood sampling and study assessments are completed.

Safety assessments include vital signs, ECG, blood samples, AE assessment, and treatment area evaluation. Treatment area evaluations including, but not limited to evaluation of edema, bruising, dysphasia, dysphonia, erythema, dyspigmentation, induration, numbness, pain, paresthesia , pruritus, skin ulceration and necrosis, injury to the marginal mandibular nerve, vascular and nerve injury and tissue damage to nearby vulnerable anatomic structures .. Concomitant medications will be recorded. An internal safety review committee will review the safety data collected during the study in a blinded manner. The committee members will include study medical monitor, Raziel's CMO and clinical director. The meeting will be held for every 40 subjects enrolled. Following completion of enrollment period, the committee will meet quarterly during the follow up period.

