#### **2.4.2 Dose Rationale**

The maximal RZL-012 dose tested in the SMF phase 2a study was 210 mg, which is 87.5% of the NOAEL. No serious AEs were associated with this dose per injection site (5mg, 0.1mL), with the distance maintained between injection sites (1cm) or with the maximal overall dose. A distance of 1 cm will allow a good distribution RZL-012 into the submental area.

The averaged doses that were injected during phase 2a study were based on injection of 32 injection points on the grid that were spread with a distance of 1cm between injection columns and rows of the SMF pattern. Therefore, in the current phase 2b study, an area which includes  $32 \pm 4$  injection points on the submental pattern grid was chosen.

For this study, two (2) doses have been chosen where the local injection volume is increased to 0.15 mL per injection site with a dose of 5.1 mg per injection site for RZL-012 low dose. Therefore, a maximal injection volume and dose will result in a maximal dose of 183.6 mg/5.4 mL into SMF area.

To increase the potential to demonstrate efficacy, a higher RZL-012 dose of RZL will also be assessed with a dose of 7.5 mg per injection site. Therefore, a maximal injection volume and dose for RZL-012 high dose will result in a maximal dose of 270 mg/5.4 mL into SMF area.

An increase from 240 mg which was determined as the NOAEL is justified based on available preclinical and clinical safety data of RZL-012.

Based on Kyebella's studies, injections up to 10 mL into the SMF area are acceptable.

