### **5.0 SAFETY ASSESSMENTS**

#### **5.1 Collection of Adverse Events Data**

Data regarding treatment-emergent AEs (TEAEs) will be collected in this study. TEAEs are events that are not present at baseline, or if present at baseline, have worsened in severity. AEs will be assessed while the subjects are in the study. AEs assessed by the Investigator as related to study drug and “ongoing” at discharge will be monitored by the Investigator until resolved or until the subject is deemed “lost to follow-up”.

Any AEs reported by the subject or noted by the Investigator or his/her designee will be recorded on the eCRF regardless of the Investigator opinion of causality. The following information will be recorded for each AE: description of the event, date and time of onset, date and time of

resolution, severity, causal relationship to study drug, outcome, action taken with the study drug and any treatment given.

The AEs reported during the trial will be graded, documented, and assessed in regards to their clinical significance and relation to study drug. Treatment area evaluations including, but not limited to evaluation of edema, bruising, dysphasia, dysphonia, erythema, dyspigmentation, induration, numbness, pain, paresthesia, pruritus, skin ulceration and necrosis, injury to the marginal mandibular nerve, vascular and nerve injury and tissue damage to nearby vulnerable anatomic structures..

All abnormal changes from baseline will be collected, graded with regards to severity or clinical significance, assessed for causal relationship and recorded on the eCRF.

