## **8.3 Study Randomization**

Subjects will be randomized to each treatment group according to a predefined randomization scheme in a ratio of 1:1:1 among eight (8) to twelve (12) clinical sites. Assignment to treatment group will be disclosed only after subject eligibility is confirmed and immediately prior to injection treatment. The Investigator, clinical staff and the subjects will be blinded to treatment group.

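### The grade 3 suspension limit in Protocol 11.2.4 does not exclude subjects dosed in the last 28 days, who cannot yet meet it, so on the plain reading it acts above 20% while enrollment is open

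*Protocol*

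**What the plan says.** Protocol 11.2.4 gives two triggers for suspending enrollment. One is more than one subject with a drug-related grade 4 or 5 event. The other, at issue here, is more than "20% of subjects report a drug related grade 3 (severe) adverse event for a period duration of more than 28 days after injection". The Synopsis repeats both.

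On timing, 11.2.4 says: "The meeting will be held when every enrolled 40 subjects completed Day 7". It adds: "Summary of the safety including all subjects up to that point may be reviewed as well". Section 2.2 has no Day 7 condition: "The meeting will be held for every 40 subjects enrolled". The Synopsis agrees with 2.2. After enrollment closes the committee meets quarterly.

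Neither place says which subjects form the denominator of the 20%, sets a minimum follow-up, or schedules a second look at the same block. The text also does not say that the rule is checked only at meetings.

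**The concern.** A subject injected within the last 28 days cannot meet the grade 3 condition. This is so whether the 28 days mean time spent at grade 3 or grade 3 still present after Day 28. While enrollment continues there are always such subjects, and the text does not take them out of the denominator. The numerator comes from one group and the denominator from a larger one, so a stated 20% becomes a higher percentage of those who could have the event.

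This is the only numerical limit for grade 3 events. Each subject has a single treatment session, so a suspension protects only people not yet dosed, and the quarterly meetings after enrollment come too late for that. The dose is also new. Section 1.2.4 reports: "A total of 92 subjects were exposed to RZL-012 at single doses of up to 240 mg". Section 2.4.2 adds: "The maximal RZL-012 dose tested in the SMF phase 2a study was 210 mg, which is 87.5% of the NOAEL". That earlier submental study used 5 mg per site. This trial goes to 270 mg at 7.5 mg per site, so how long severe reactions persist at this dose has not been observed.

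**Working it through.** **Inputs.** The plan gives no derivation for the 20%, so there is no figure of its own to reproduce.
- Reviews at n = 40, 80 and 120 of 135 subjects, each at Day 7 of the nth subject (11.2.4, 12.1).
- More than 20% means at least 9 of 40, 17 of 80 and 25 of 120.
- Accrual is not stated. Section 8.3 randomizes "in a ratio of 1:1:1 among eight (8) to twelve (12) clinical sites". I assume even accrual of r = 2 to 12 a week, roughly one per site per month at 8 sites to one per site per week at 12.
- A subject is assessable at 29 or more days after injection.

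**Step 1: assessable subjects.** At the review, subject k has 7 + 7(n − k)/r days of follow-up. Requiring at least 29 gives n − k ≥ 22r/7, so E = floor(n − 22r/7). The effective limit is the number needed divided by E.

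| r per week | E at 40 | 9/E | E at 80 | 17/E | E at 120 | 25/E |
|---|---|---|---|---|---|---|
| 2 | 33 | 27.3% | 73 | 23.3% | 113 | 22.1% |
| 4 | 27 | 33.3% | 67 | 25.4% | 107 | 23.4% |
| 6 | 21 | 42.9% | 61 | 27.9% | 101 | 24.8% |
| 8 | 14 | 64.3% | 54 | 31.5% | 94 | 26.6% |
| 10 | 8 | over 100% | 48 | 35.4% | 88 | 28.4% |
| 12 | 2 | over 100% | 42 | 40.5% | 82 | 30.5% |

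The 10-a-week entry at the first review depends on rounding. Counting strictly more than 28 days, with the day count not rounded up to 29, gives 9 assessable, all of whom would need the event. Using 40 is also the milder choice: counting everyone dosed by then (n + r) at 6 a week needs 10 of 46, and 10/21 = 47.6%.

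**Step 2: continuous checking.** With N dosed, about 4r fall in the last 28 days. At N = 80 the limit acts as 17/(80 − 8) = 23.6% at 2 a week and 17/(80 − 16) = 26.6% at 4. The effect remains.

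**Step 3: chance of crossing at an assumed true pooled rate of 30%.**
- First review: P(Bin(33, 0.30) ≥ 9) = 0.70 at 2 a week, P(Bin(27, 0.30) ≥ 9) = 0.42 at 4, P(Bin(14, 0.30) ≥ 9) = 0.01 at 8. With all 40 past Day 28 it would be P(Bin(40, 0.30) ≥ 9) = 0.89.
- By the second review (simulation): 0.93 at 2 a week, 0.84 at 4, 0.25 at 10, with n + r = 82, 84 and 90 dosed.
- By the third review: 0.98, 0.96 and 0.67, with 122, 124 and 130 dosed.

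**Step 4: a true pooled rate of 10%.** With all 40 past Day 28, P(Bin(40, 0.10) ≥ 9) is about 0.015. Under the present timing it is about 0 to 0.005.

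**Step 5: the other reading.** If only assessable subjects count at the Day 7 meeting, the limit stays near 20% (7/33 = 21.2% at 2 a week) but can rest on few people. At 10 a week, 2 of 8 crosses, and at a true 10% that has probability P(Bin(8, 0.10) ≥ 2) = 0.19.

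**Step 6: timing of a later check.** When subject 40 reaches Day 29, 40 + floor(29r/7) are dosed: 56 at 4 a week, 81 at 10. Waiting for the Day 56 visit gives 40 + 8r: 72 and 120.

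**The case against.** The strongest reply is that the text leaves the denominator open and does not set a higher limit. A committee that counts only followed subjects applies something close to 20%. That stands as a statement about wording, but the protocol does not instruct it. Step 5 also shows that the Day 7 timing then leaves a thin base under fast accrual.

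A second reply is that the trigger can operate between meetings. That is a fair reading, but it does not remove the effect (Step 2).

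Third, the size depends on an accrual rate that nobody has stated, and the most striking figures need 8 to 12 a week in a trial with two screening visits, MRI and laboratory exclusions. That stands. A reader might infer that the first review cannot trigger at all. The documents do not support this, because it requires about 10 or more a week and turns on rounding.

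Fourth, a pooled 30% is a severe scenario. With 1:1:1 allocation and no placebo events it means 0.30 × 3/2 = 45% of active subjects. In the submental Phase 2a study the severe edema and induration were severe only in the first 24 hours, and 1.2.4 counts 10 subjects with severe events across all studies. This stands too: 30% shows how the rule behaves and is not a forecast.

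Finally, there are other protections: the grade 4/5 limb, termination for recurring severe reactions (2.4.3), termination by the investigator or ethics committee (9.0), and AE summaries at each meeting. These limit the harm but do not repair the numerical limit. A reader might also infer that brief severe swelling would be miscounted as persistent. Nothing in the documents shows that, and the 28-day condition looks deliberate.

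**Conclusion.** The point holds as a mismatch between the follow-up the grade 3 limb needs and the subjects it is applied to. If all dosed subjects count, the limit acts above 20% at every accrual rate while enrollment is open. How far above depends on assumed even accrual. The gap is widest at the first review and narrows by the third.

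At 2 to 4 a week the consequence is mainly delay, with about 40 more subjects dosed between the first and second reviews. At around 10 a week, most of the trial could be dosed before the limit acts. If the true rate of persistent grade 3 events is near 10%, nothing practical changes. Severity is minor to moderate: the probable effect is limited, but the correction is cheap and bears on subject safety.

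**What to change.** In 11.2.4 and the Synopsis:

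1. Define the denominator of the grade 3 limb as subjects with more than 28 days of follow-up after injection.
2. Make review of all subjects to date mandatory at each meeting.
3. Keep the Day 7 meeting for acute events and the grade 4/5 limb.
4. Re-check the grade 3 limb on accumulating data once each block of 40 has passed Day 28.

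The re-check needs no eCRF change. Section 5.1 already records onset date, and its list continues with "resolution, severity, causal relationship to study drug, outcome, action taken with the study drug and any treatment given". An event seen at the Day 28 visit has not yet lasted more than 28 days, and the next scheduled visit is Day 56. Any grade 3 event ongoing at Day 28 should therefore be confirmed by a follow-up contact shortly afterwards.

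The cost is a few sentences, one extra data check per block, and a noisier limit whenever few subjects are assessable. The check falls 22 days after the Day 7 meeting (Day 29 against Day 7), which is why that meeting should stay. The 20% threshold itself is a clinical judgment and need not change.

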## **12.0 STATISTICAL CONSIDERATIONS**

### **12.1 Sample Size Determination**

A total of 135 subjects will be included in the study, divided into three (3) groups: RZL-012 low dose (up to 183.6 mg/5.4 mL), RZL-012 high dose (up to 270 mg/5.4 mL) and placebo (up to 5.4 mL) with 45 subjects in each group.

For the primary endpoint (proportion of high dose group subjects who have at least a 1-grade improvement from baseline to Day 84 on the C-CAT scale), the assumed true rates are 70% in the RZL-012 high dose group and 35% in the placebo group (a difference of 35 percentage points). Based on the use of a two-sided test of equality of binomial proportions at the alpha=0.05 level of significance, 41 subjects per group are required at 90% power. In order to account for a dropout rate of up to ~9%, the planned sample size is 45 subjects per group, for a total sample size of 135 subjects.

### **12.2 Analysis Data Sets**

Subjects who receive study treatment will be included in the safety analyses.

### **12.3 Endpoints Analyses**

All measured variables and derived parameters will be listed individually and, if appropriate, tabulated by descriptive statistics.

For categorical variables, summary tables will be provided giving sample size, absolute and

relative frequency, and 95% confidence interval (CI) for proportions by study arm.

For continuous variables, summary tables will be provided giving sample size, arithmetic mean, standard deviation, coefficient of variations (CV%), median, minimum and maximum, and 95% CI for means of variables by study arm.

The data will be analyzed using the SAS version 9.4 (SAS Institute, Cary North Carolina).

For the primary endpoint analysis, Pearson's chi-square test will test the statistical significance of the difference in the proportion of responding subjects between the high dose RZL-012 group and the placebo group. A responder is defined as a subject who has at least a 1-grade improvement between Day 84 and baseline on the C-CAT.

Secondary endpoints (improvement in 1 point in S-CAT and C-CAT, improvement in 2 points in both S-CAT and C-CAT) will be tested using a two-sided test of equality of binomial proportions at the alpha=0.05 level of significance. If the primary analysis is not statistically significant, then the results of the secondary analysis will be exploratory rather than confirmatory.

All other secondary endpoints will be tested using a two-sided test at the alpha=0.05 level of significance.

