Statistical Analysis	
A sample size of 135 subjects will be included in the study, divided into three (3) groups: RZL-012 low dose (up to 183.6 mg/5.4 mL), RZL-012 high dose (up to 270 mg/5.4 mL) and placebo (up to 5.4 mL), with 45 subjects in each group.
 
For the primary endpoint (proportion of high-dose group subjects who have at least a 1-grade improvement from baseline to day 84 on the C-CAT scale), the assumed true rates are 70% in the RZL-012 high dose group and 35% in the placebo group (a difference of 35 percentage points). Based on the use of a two-sided test of equality of binomial proportions at the alpha=0.05 level of significance, 41 subjects per group are required at 90% power. In order to account for a dropout rate of up to ~9%, the planned sample size is 45 subjects per group, for a total sample size of 135 subjects.
 
Secondary endpoints (improvement in 1 point in S-CAT and C-CAT, improvement in 2 points in both S-CAT and C-CAT) will be tested using a two-sided test of equality of binomial proportions at the alpha=0.05 level of significance. If the primary analysis is not statistically significant, then the results of the secondary analysis will be exploratory rather than confirmatory. All secondary endpoints will be tested using a two-sided test at the alpha=0.05 level of significance.
 
All other secondary endpoints will be tested using a two-sided test at the alpha=0.05 level of significance.
 
All measured variables and derived parameters will be listed individually and, if appropriate, tabulated by descriptive statistics.
 
For categorical variables, summary tables will be provided giving sample size, absolute and relative frequency, and 95% confidence interval (CI) for proportions by study arm.
 
For continuous variables, summary tables will be provided giving sample size, arithmetic mean, standard deviation, coefficient of variations (CV%), median, minimum and maximum, and 95% CI for means of variables by study arm.
 
The data will be analyzed using the SAS version 9.4 (SAS Institute, Cary North Carolina).
 
For the primary endpoint analysis, Pearson's chi-square test will test the statistical significance of the difference in the proportion of responding subjects between the high dose RZL-012 group and the placebo group. A responder is defined as a subject who has at least a 1-grade improvement between Day 84 and baseline on the C-CAT.

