### **2.3.2 Secondary Endpoints**

The secondary endpoints of this study are as follows:

- Proportion of subjects who have at least a 1-grade improvement in both the C-CAT and S-CAT (Day 84 versus baseline) in the RZL-012 groups versus placebo group.
- Proportion of subjects who have at least a 2-grade improvement in both the C-CAT and S-CAT (Day 84 versus baseline) in the RZL-012 groups versus placebo group.
- Reduction in SMF volume by MRI (Day 84 versus screening) in the RZL-012 groups versus placebo group.
- Reduction in SMF thickness measured with caliper (Day 84 versus baseline) in the RZL-012 groups versus placebo group. Safety assessment of RZL-012 in the treatment of SMF reduction.
- safety of RZL-012 in the treatment of SMF reduction.

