## 5. PROCEDURE

- **Introduction**

This Statistical Analysis Plan (SAP) is based on **RZL-012-SMF-P2bUS-001** study protocol version 1.6, dated 08 March 2022

This Statistical Analysis Plan (SAP) contains details of the statistical analyses that will be performed, providing a more detailed description of the approach defined in the study protocol. Definitions of variables and populations used for the analyses are also included. The SAP will be finalized and signed prior to hard lock of the database.

General output specifications are provided; examples are given of calculations of derived variables.

- **Study Objectives and Endpoints**

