## 6. STATISTICAL ANALYSIS

- General

All measured variables and derived parameters will be listed individually and, if appropriate, tabulated by descriptive statistics.

For categorical variables, summary tables will be provided giving sample size, absolute and relative frequency and 95% CI (Confidence Interval) for proportions by study group.

For continuous variables, summary tables will be provided giving sample size, arithmetic mean, standard deviation, coefficient of variation (CV%), median, minimum and maximum and 95% CI (Confidence Interval) for means of variables by study group.

All tests will be two-tailed, and a p value of 5% or less will be considered statistically significant.

The data will be analyzed using the SAS ® version 9.4 (SAS Institute, Cary North Carolina).

Statistical methods presented in the SAP may be slightly different from those that are presented in the protocol. Differences are clearly stated and the SAP supersedes the protocol only with regard to the way data will be handled and analysed.

- Subject Disposition

A detailed description of subject accountability including count of subjects included, exposed, completed (i.e., subjects who complete the study treatment) and discontinued along with the main reason for discontinuation will be generated for each treatment group and for all subjects. All withdrawals from the study, taking place on or after study drug injection, will be fully documented in the body of the Clinical Study Report.

Demographic and Baseline Characteristics

MediStat Statistics in Medicine	DOCUMENT NUMBER: 140-BST-PLN-001	PAGE: 14 of 16
TITLE: Statistical Analysis Plan of Protocol Number RZL-012-SMF-P2bUS-001	EFFECTIVE DATE : 08/03/2022 REVISION NUMBER : 1.0	

Baseline will be defined as the last available and evaluable parameter value before and closest to the injection. If a rechecked value is used for baseline, it should be collected under the same conditions as for the planned baseline.

Baseline safety data will be presented along with subsequent safety values assessed during or after dosing.

- **Analysis of Efficacy for Primary Endpoint**

The proportion of subjects who have at least a 1-grade improvement in the C-CAT on Day 84 versus baseline will be calculated for the placebo group and the RZL-012 high-dose group along with 95% Confidence interval for proportion.

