The Chi-Square test will be applied to test the statistical difference between the placebo group and the RZL-012 high-dose group in responder rate at Day 84. Responder rate is defined as the percentage of subject achieving at least a 1-grade improvement from baseline in C-CAT.

- **Analysis of secondary Endpoints**

Secondary endpoints (improvement in 1 point in S-CAT and C-CAT, improvement in 2 points in both S-CAT and C-CAT) will be tested using a two-sided test of equality of binomial proportions at the alpha=0.05 level of significance.

All other secondary endpoints will be tested using a two-sided test at the alpha=0.05 level of significance.

- The Chi-Square test will be applied to test the statistical difference between the placebo group and each of the RZL-012 dose groups in the responder rate at Day 84 where responder rate is defined as the percentage of subject achieving at least a 1-grade improvement from baseline in both S-CAT and C-CAT.
- The change and percentage of change from baseline at Day 84 in SMF thickness measured with caliper and in SMF volume by MRI will be calculated along with 95% Confidence intervals.

The Paired T-test for two means (paired observations) will be applied for testing the statistical significance of the change and percentage of change from baseline at Day 84 in SMF thickness measured with caliper and in SMF volume by MRI within each study group.

MediStat Statistics in Medicine	DOCUMENT NUMBER: 140-BST-PLN-001	PAGE: 15 of 16
TITLE: Statistical Analysis Plan of Protocol Number RZL-012-SMF-P2bUS-001	EFFECTIVE DATE : 08/03/2022 REVISION NUMBER : 1.0	

The two-sample T-test for independent samples will be applied for testing the statistical significance of the change and percentage of change from baseline at Day 84 in SMF thickness measured with caliper and in SMF volume by MRI between each of the RZL-012 dose groups and the placebo group.

- Analysis of Exploratory endpoint
  - SMF improvement

The SMF improvement using the Global Aesthetic Improvement Scale (GAIS) , the physician Global Assessment of Change Scale, Subjects Global Self-Assessment of Change Scale, Subject Global Assessment of Change Scale, the subject's satisfaction questionnaires, and the subjects's impact questionnaire will be summarized at each timepoint and by treatment group.

- Analysis of Safety

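### After a significant primary, the secondaries are implicitly confirmatory, yet both doses are tested on four endpoints at 0.05 each, with no order or adjustment

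*Protocol*

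**What the plan says.** The primary is one comparison, high dose versus placebo, on the proportion with at least a 1-grade C-CAT improvement at Day 84.

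Protocol 2.3.2 lists four secondary efficacy endpoints: the 1-grade composite of C-CAT and S-CAT, the 2-grade composite, SMF volume by MRI and caliper thickness. Each is defined for both doses, for example "2-grade improvement in both the C-CAT and S-CAT (Day 84 versus baseline) in the RZL-012 groups versus placebo group".

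On significance, the Protocol Synopsis says "All secondary endpoints will be tested using a two-sided test at the alpha=0.05 level of significance". Protocol 12.3 and the Synopsis add one condition: "If the primary analysis is not statistically significant, then the results of the secondary analysis will be exploratory rather than confirmatory". In 12.3 this closes the paragraph on the two composites; MRI and caliper follow separately.

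SAP section 6, Analysis of secondary Endpoints, carries the sentence that precedes the condition in the protocol ("Secondary endpoints (improvement in 1 point in S-CAT and C-CAT, improvement in 2 points in both S-CAT and C-CAT) will be tested") and the one that follows it ("All other secondary endpoints will be tested using a two-sided test at the alpha=0.05 level of significance"), but not the condition. SAP section 6, General, adds "All tests will be two-tailed, and a p value of 5% or less will be considered statistically significant" and says of departures from the protocol: "Differences are clearly stated and the SAP supersedes the protocol only with regard to the way data will be handled and analysed". SAP section 5, Introduction, describes the SAP as "providing a more detailed description of the approach defined in the study protocol".

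Neither document gives a testing order, an alpha split or an adjustment among the secondaries.

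**The concern.** A rule that demotes the secondaries when the primary fails has meaning only if they rank higher when it succeeds. After a success, however, nothing limits error across them.

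The low dose is the weak point. It is not part of the primary, so a true high-dose effect opens confirmatory status for low-dose claims without any low-dose test having been passed. A chance low-dose result, or a chance result on one endpoint, could then be reported as confirmed.

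An analyst working only from the SAP would also not see the condition. The omission is not listed as a difference from the protocol.

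**Working it through.** **The plan's own figure.** Inputs from Protocol 12.1: 70% versus 35%, two-sided 0.05, 90% power. With pooled variance under the null, the mean rate is 0.525 and

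n = [1.96·√(2·0.525·0.475) + 1.2816·√(0.70·0.30 + 0.35·0.65)]² / 0.35² = (1.384 + 0.848)² / 0.1225 ≈ 40.7, so 41 per group.

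This matches. Planning 45 allows a loss of 1 − 41/45 = 8.9%. The documents give no error figure for the secondaries.

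**Count of comparisons.**
- Four endpoints × two doses = 8. The SAP spells out tests of each dose for the 1-grade composite, MRI and caliper. For the 2-grade composite they follow from the endpoint wording.
- If the condition covers only the two composites: 2 × 2 = 4, of which 2 are low-dose.
- The SAP tests MRI and caliper on change and on percentage change. Between-group tests are therefore 4 (composites) + 2 measures × 2 scales × 2 doses = 12. The within-group paired t-tests add 3 arms × 2 measures × 2 scales = 12.

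**When the primary null is true.** A confirmatory secondary claim needs a significant primary, so the risk is at most about 5%. Simulation gives 2.0-4.0%.

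**When the primary succeeds and the low dose does nothing.** Each subject has four latent normal scores (C-CAT, S-CAT, MRI, caliper) with common within-subject correlation r.
- From the documents: 45 per arm, and C-CAT responder rates of 70% (high dose) and 35% (placebo).
- Assumed: r; placebo rates per scale of 35% for 1 grade (the C-CAT rate applied to S-CAT as well) and 10% for 2 grades; the low dose identical to placebo on everything.
- Tests: Pearson chi-square for the composites, two-sample t for MRI and caliper on one scale each. 40,000 trials per setting; primary power 0.92.

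Chance of at least one low-dose p≤0.05, given a significant primary:

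| Assumed r | 0 | 0.3 | 0.5 | 0.7 | 0.9 |
|---|---|---|---|---|---|
| Any of four, two-sided (single test: 5%) | 14.6% | 14.8% | 15.0% | 15.6% | 14.0% |
| Any of four, in the drug's favour (single test: 2.5%) | 7.7% | 8.0% | 8.2% | 8.6% | 7.7% |
| Two composites only, two-sided | 5.5% | 6.1% | 7.3% | 8.9% | 10.1% |

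For the composites in the drug's favour only, the range is 3.0% to 5.7%. Repeat runs agree within about half a percentage point.

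The composite row rises with r because the 2-grade composite is very rare when the scales are weakly related (placebo rate about 1% at r=0, about 7% at r=0.9). At low r its chi-square test almost never rejects.

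**How plausible all four nulls are.** Protocol 1.2.4.1.4 reports a mean MRI volume change of -22.2% in the higher-dose Phase 2a cohort, which averaged 158.5 mg, against -0.4% on placebo. By total dose, this trial's low dose (163.2±20.4 mg) is close to that cohort. An MRI effect at the low dose is therefore likely, and the four-endpoint rows are an upper case.

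**The case against.** **Confirmatory status is only inferred.** True: neither document says that the secondaries are confirmatory after a success. But the protocol draws the distinction itself, and its sentence has no purpose otherwise.

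**The condition may cover only the composites.** This stands as an open reading. In 12.3 the sentence belongs to the composites' paragraph. In the Synopsis the same paragraph goes on to speak of all secondary endpoints. On the narrow reading the excess is small over much of the range, particularly in the drug's favour.

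**A low dose significantly worse than placebo would never be reported as a success.** This stands, so the favourable-direction figure of about 8% against 2.5% fits the stated harm better than 14-16%.

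**The scenario is extreme.** This also stands, because of the Phase 2a MRI result.

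**The SAP omission is a copying slip.** Probably so: the SAP presents itself as elaborating the protocol. But it also says that differences are stated, and this one is not.

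**This is Phase 2b, the single primary is intact and one sentence would cure the problem.** That limits the weight of the point. It does not settle what a secondary p value will mean.

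**Conclusion.** The point holds as a gap in the rule that applies after a significant primary. The status of the secondaries is implied, their scope is unclear and no procedure limits error across them, least of all for the low dose. The upper case is about 14-16% two-sided and about 8% in the drug's favour. On the composites alone it is about 5.5-10% (3-6% favourable). These figures rest on the assumed correlations and 2-grade placebo rate, and on a low dose with no effect on the endpoints counted.

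A reader might infer more, but the documents do not support it:
- **The primary is compromised.** It is one test and its error rate is unaffected.
- **The low-dose risk is 1 − 0.95⁴ = 18.5%.** That treats the four tests as independent and each at its full 5%. But the 2-grade composite is nested in the 1-grade composite, and its test rejects less than 5% of the time when the event is rare.
- **The SAP has abolished the condition,** giving 16.5-31.7% if all eight nulls hold (correlation 0.9 to 0, normal model). The SAP's description of itself points the other way.
- **Twenty-four tests compete for confirmatory claims.** The paired tests are not secondary endpoints, which are all defined against placebo. Change and percentage change are two scales of one measure.

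The sponsor should correct this, but it does not threaten the main result.

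**What to change.** Before unblinding:

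1. Copy the conditional sentence into SAP section 6, Analysis of secondary Endpoints. State in both documents which secondaries it covers, naming MRI and caliper as in or out.
2. Choose one of the following:
   - (a) State in both documents that all secondary p values are nominal, and drop the implied confirmatory status.
   - (b) If confirmatory claims are wanted after a significant primary, prespecify a fixed sequence, or Holm, across the named dose-versus-placebo comparisons. Use one pre-chosen scale each for MRI and caliper. Label the other scale and the within-group paired tests descriptive.

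**Cost.** Only wording changes. Option (a) costs no power. Under (b), some results with p≤0.05 become nominal:
- **Holm over eight.** If the high-dose 1-grade composite were 55% versus 20% (assumed), exact chi-square power at 45 per arm is 94% at 0.05 and 78% at Holm's opening level of 0.05/8.
- **Fixed sequence.** That endpoint keeps 94% if placed at the head, but one failure makes every later test nominal. With all high-dose tests ahead of the low dose, the rare high-dose 2-grade composite could block every low-dose claim. If placebo were 5% (assumed), its power is 39%, 63% or 81% for high-dose rates of 15%, 20% or 25%. The sponsor should check this before choosing its position.
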